## **9. Research Questions:** The current study’s research questions are as follows:

- 1) Will the ***Shauriana*** intervention be acceptable, feasible, and safe?

2) What effect will this intervention have on PrEP uptake and adherence, compared to standard care?

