reviewed by the team and discussed at weekly meetings. At the conclusion of the pilot study, we will assess whether we need to revise the intervention based on pilot test findings. If this is the case, we will submit revisions to the ethical review board at Maseno University and to the human subjects research committee at the University of Washington for approval.

**Aim 2 Procedures: RCT of the Shauriana Intervention.** Aim 2 work will use an RCT design to test the acceptability, feasibility, and safety of the **Shauriana** Intervention compared to standard care and estimate initial effect size. Acceptability will be assessed using Likert scales in participant ACASI questionnaires and qualitative exit interviews with participants in each study arm. Feasibility will be assessed at regular research team and peer facilitator meetings, which will be minuted. Safety will be assessed through careful monitoring of study participants to identify and report any adverse events. Information on perceived or experienced social harms and benefits will be collected by study staff at all clinic visits and assessed in greater depth in qualitative exit interviews. Additional trial outcomes that will be monitored and reported include screening and enrollment numbers, visit and intervention attendance, overall retention, and self-reported PrEP uptake and adherence. At the end of the trial, urine samples will be tested for tenofovir (TFV) drug levels (see Laboratory details, below). Dried blood spots will also be collected and stored for future testing of TFV-DP and FTC-TP levels, should funding permit.

Recruitment. The **Shauriana** Intervention pilot RCT will enroll 60 HIV-negative men (30 in the intervention and 30 in SOC) and follow participants for 6 months. We will recruit 60 participants over the course of 3 months; this target is realistic, given enrolment of over 160 men in the **Anza Mapema PrEP** cohort within a 2-month period. Potentially eligible participants will be recruited by NYARWEK, then referred to the **Anza Mapema** Clinic for screening and consenting, as described on pp. 11-12.

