**Table 2. PrEP-oriented and *Shauriana*-Specific Data Elements for Collection by ACASI**

Data Element	Content	Method	Frequency
Primary Outcome Variables			
Acceptability	5-point Likert scales evaluating acceptability of the Shauriana intervention components,  exit interviews for detailed qualitative feedback	ACASI, exit interviews	Quarterly
Feasibility	Visit attendance, session delivery, documentation of peer contacts, minutes of research team meetings	Clinic and intervention data, minutes	Ongoing
Safety	Adverse events reported by participants or study staff; self-reported consequences of study participation in exit interviews	Reports at clinic visits, exit interviews	M1 then quarterly
Secondary Outcome Variables			
PrEP uptake	Two questions on past and ongoing PrEP use	ACASI	Quarterly
PrEP adherence	A series of self-report measures we have used in previous work.	ACASI	Quarterly
PrEP refills	Documented at Anza Mapema for each participant	Clinic data	Quarterly
PrEP drug levels	Urine TFV levels  DBS TFV-DP and FTC-TP levels (if funding permits)	Laboratory	Quarterly
Potential Correlates of Retention and Adherence			
Risk perception	A question on the participant’s self-assessment of his chance of getting HIV/AIDS	ACASI	Quarterly
PrEP knowledge	PrEP knowledge questions (based on relevant literature and completed qualitative research by the team)	ACASI	Quarterly
Motivation/skills	LifeWindows Information-Motivation-Behavioral Skills adherence questionnaire,  adapted for PrEP use based on completed qualitative research by the team.	ACASI	Quarterly
PrEP distrust	PrEP-related distrust, skepticism, trust in providers, and ownership (championing) per [name] et al. 	ACASI	Quarterly
Shared decision making	Participant-reported sharing of decision-making related to PrEP; adapted from Barr et al. 	ACASI	Quarterly
Social support and loneliness	Multidimensional Scale of Perceived Social Support, a 12-item scale of perceived support from family, friends, others 	ACASI	Quarterly
Self-esteem	10-item Rosenberg self-esteem scale,  previously used in this population 	ACASI	Quarterly
Resilience	Coping self-efficacy scale: 13-item version validated in HIV+ GBMSM with depressed mood 	ACASI	Quarterly

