All participating men will receive a comprehensive package of services, including HIV testing and risk reduction counseling, condoms and lubricants, and screening and treatment for syndromic STI, regardless of whether they initiate and continue PrEP. For men who initiate and continue PrEP, appropriate clinical and laboratory monitoring will minimize the risk of severe adverse events. Men in the standard care and intervention arms will receive regular PrEP adherence support, according to detailed procedures for each study arm. There will be no charge to participants for the medications or services provided. Men may withdraw from the study at any time. For any man who withdraws from the study, we will ask him to complete a withdrawal survey regarding his reason for withdrawal, any care and referral needs, and intent to establish care elsewhere. Men who withdraw will also be invited to participate in an exit interview, if willing. Of note, PrEP is available in a non-research (program) context at several sites in Kisumu including the *Anza Mapema* Clinic, should men be eligible for and interested in PrEP but not want to participate in this research study.

**Potential Benefits to the Subjects and Others:** Benefits of study participation include the following:

1. All study participants may benefit in terms of access to risk reduction counseling, periodic STI screening and HIV testing, and PrEP programming.
2. For study participants who initiate and adhere to PrEP during follow-up, there is the potential to avoid HIV acquisition while working to reduce behavioral risks.
3. Pilot study participants and those assigned to the *Shauriana* intervention group in the randomized trial may benefit from a GBMSM-affirming, tailored approach to PrEP provision with activities to promote resilience, decrease stigma, and improve sexual health.
4. All participants will contribute to a study that will evaluate ways of increasing access to HIV prevention services tailored to the needs of Kenyan GBMSM.

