### **13. Data Management & Statistical Analysis Plans:**

**Data Management Plan:** Recruitment, consenting, and data collection will be monitored carefully to ensure the confidentiality and safety of participants, as detailed in our Human Subjects statement.

**Statistical Analysis Plan:** Data analysis will include both quantitative and qualitative components.

**Qualitative analyses.** Clinic staff and intervention team feedback from meetings will be monitored in real time, to identify any problems needing correction, and then analyzed at the end of the study, to assess feasibility of the intervention, should scale-up for a larger trial seem warranted. Pilot study feedback and pilot/RCT exit interviews will be analyzed to evaluate men’s views regarding the acceptability and overall value of the intervention vs. standard care. In addition, we will review exit interview transcripts to identify best practices for engaging and retaining GBMSM in the **Shauriana** intervention and for optimizing adherence to a daily PrEP regimen and uptake of other HIV prevention services. Notes and tapes from exit interviews will be translated and transcribed into English, then reviewed to identify and code salient themes. NVivo software will be used to facilitate qualitative analysis.

**Primary quantitative analyses.** Acceptability of intervention procedures will be assessed by comparing month 3 and month 6 Likert scale scores for the acceptability of study participation across study arms, using Mann-Whitney U tests. Likert scale scores for **Shauriana** intervention components will be summarized using medians, interquartile ranges, and ranges for intervention participants. Social harms and benefits reported by participants in each arm will be tallied and described in report form.

**Secondary quantitative analyses.** Participant characteristics in the two study arms will be presented using counts and percentages for categorical variables and means and standard deviations or medians and inter-quartile ranges (IQR) for continuous variables. Descriptive statistics will be used to evaluate distributions of the measures assessed at each time-point. To determine validity of the scales used, item scores will be evaluated using Cronbach’s alpha and factor analysis, then compared to published scale psychometrics in African populations if possible. The temporal stability of scales will also be investigated to ensure reliability. These

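### Acceptability: the between-arm rank test named as its assessment is not the Table 2 outcome, and neither that comparison nor the component ratings has an interval estimate (minor)

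*Combined protocol and SAP*

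**What the plan says.** Research question 1 (Section 9) asks whether the "intervention be acceptable, feasible, and safe". Table 2 in Section 11 lists acceptability as a primary outcome with two parts: "5-point Likert scales evaluating acceptability of the" Shauriana components, and "exit interviews for detailed qualitative feedback".

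Under the primary quantitative analyses, Section 13 says that acceptability of intervention procedures is assessed by "comparing month 3 and month 6 Likert scale scores for the acceptability of study participation across study arms, using Mann-Whitney U tests". The next sentence says that scores for Shauriana "intervention components will be summarized using medians, interquartile ranges, and ranges for intervention participants". The qualitative plan in the same section has exit interviews analysed for men's views "regarding the acceptability and overall value of the intervention vs. standard care".

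The Aim 2 procedures in Section 11 describe the trial as testing acceptability against standard care, with Likert scales and exit interviews in each arm. The power paragraph in Section 11 says the trial is neither designed nor powered to determine the overall intervention effect or the effects of components. It hopes the results will inform larger-scale testing.

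**The concern.** Two different quantities carry the label of acceptability. One is how the intervention arm rates the Shauriana components, which is the Table 2 definition. The other is how the two arms rate taking part in the study, which is what the named test compares. Standard-care men are not assigned Shauriana, so the test cannot be run on the Table 2 ratings.

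A rank test answers a comparative question. It does not say whether acceptability is high or low, and its p-value does not show how large a difference the data still allow. With about 25 to 30 men per arm, a non-significant result is likely even for a moderate difference, and it could be misread as equal acceptability. The component summary does speak to level, but it has no interval to show how firmly some 25 ratings fix that level. The investigators who design the larger study will need both the estimate and its uncertainty.

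**Working it through.** The plan gives no power, alpha, effect size or precision for acceptability, so there is no figure of its own to reproduce. All score counts below are assumptions for illustration.

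**Inputs from the document.** 30 men per arm (Section 11, Recruitment under Aim 2). Retention was 85% in the earlier Shikamana pilot trial and 83% at month 12 in the earlier Kisumu cohort (Section 8). Applied here, 0.85 × 30 = 25.5 and 0.83 × 30 = 24.9, so about 25 raters per arm is a reasonable assumption.

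**1. What the rank test shows.** Assume one 5-point participation score and 25 men per arm.
- Intervention: 5 threes, 10 fours, 10 fives (20/25 score 4 or 5).
- Standard care: 7 threes, 10 fours, 8 fives (18/25 score 4 or 5).
- Pairs in which the intervention man scores higher: 10 × 7 + 10 × 17 = 240.
- Tied pairs: 5 × 7 + 10 × 10 + 10 × 8 = 215.
- U = 240 + 215/2 = 347.5. Its null mean is 625/2 = 312.5 and its tie-corrected SD is 48.2. With continuity correction, z = (35 − 0.5)/48.2 = 0.72 and p = 0.47.
- Take 2 points off every score in both arms: U and p do not change. The test compares arms and carries no information on level.

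**2. What an estimate would add.** The probability that an intervention man scores higher than a standard-care man, with ties counted as half, is U/(25 × 25) = 347.5/625 = 0.556. The DeLong-type SE is 0.077, so the 95% CI is 0.556 ± 1.96 × 0.077, or 0.40 to 0.71. The same data that give p = 0.47 are compatible with a modest disadvantage and with a sizeable advantage.

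**3. Power of the rank test.** Assume two-sided 5% alpha, a shift of 0.5 SD and the usual 0.955 efficiency under normality. Power ≈ Φ(0.5 × √(0.955n/2) − 1.96).
- n = 30 per arm: Φ(1.89 − 1.96) = 47%.
- n = 25 per arm: Φ(1.73 − 1.96) = 41%.

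**4. Precision of the level.** The Clopper-Pearson limits for x favourable of n are the 2.5% point of Beta(x, n − x + 1) and the 97.5% point of Beta(x + 1, n − x).

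| Favourable/raters | Share | Exact 95% CI |
|---|---|---|
| 25/30 | 83% | 65% to 94% |
| 21/25 | 84% | 64% to 95% |
| 16/20 | 80% | 56% to 94% |

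**5. Why the number of raters matters.** If 30 are assigned and 25 rate, 21 favourable ratings give 21/30 = 70% if all five missing ratings are unfavourable, and 26/30 = 87% if all are favourable. Early withdrawals are replaced and the replacements are randomised afresh (Section 11, Recruitment), so the number assigned to the intervention need not be exactly 30.

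**The case against.** The strongest reply is that the between-arm comparison is what the trial set out to do. The Aim 2 procedures describe a test of acceptability against standard care, with data from each arm, and the exit-interview analysis makes the same contrast. That stands. The comparison should remain, and moving it to a supporting role would be a preference rather than a correction.

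A reader might infer that the Table 2 outcome goes unanalysed, or that the level of acceptability would never be seen. The documents do not support this. Component medians, IQRs and ranges are planned under the primary heading, Section 13 also plans descriptive distributions of the measures at each time-point, and exit interviews have their own analysis. Nor is drop-out ignored. Section 11 monitors "screening and enrollment numbers, visit and intervention attendance, overall retention, and self-reported PrEP uptake and adherence", Section 13 compares retention by arm, and a man who leaves is asked to "complete a withdrawal survey regarding his reason for withdrawal".

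A reader might also treat the lack of a designated primary visit, a stated rater count or a participation item in Table 2 as defects. No decision rule depends on one visit. The realised number of raters cannot be known in advance, and the planned arm size is given. The participation item may be in Appendix F, which was not available for review. These are matters of detail.

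Finally, a proportion scoring 4 or 5 presumes a single 5-category item. The plan speaks of scales and proposes Cronbach's alpha and factor analysis, so the ratings may be multi-item scores. That stands too: any cut-off must suit the actual scoring.

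The reply leaves one gap. Neither the test nor the component summary is given an interval estimate.

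**Conclusion.** The point holds, and it is minor. Section 13 attaches the assessment of intervention acceptability to a between-arm test of study-participation scores, while Table 2 defines the outcome on component ratings from the intervention arm alone. Both quantities are planned for analysis and no data would be lost. The weakness is that the comparison is specified only as a test, in a trial not powered for effects, and that the level is to be summarised without a confidence interval.

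The size is illustrative: an observed 84% favourable would carry an interval from 64% to 95%, and p = 0.47 would leave a probability of superiority anywhere from 0.40 to 0.71. These figures rest on about 25 raters per arm, invented score counts and a single 5-point item. They show the order of the uncertainty and do not predict this trial's results.

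**What to change.** Amend the primary quantitative analyses in Section 13 in two places.

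1. State that the intervention-arm component ratings, as defined in Table 2, are the primary quantitative measure of the level of acceptability. Keep the median and IQR and add a 95% CI, for example an exact interval for the proportion rating favourably at a cut-off fixed in advance and suited to the scale's scoring. Report the number of raters out of all men assigned to the intervention.
2. Keep the between-arm comparison of study participation as the planned contrast with standard care. Report with it an effect estimate and 95% CI, for example the probability that an intervention man scores higher, with ties counted as half. Say that a non-significant p-value will not be read as equal acceptability.

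Naming a primary visit and pointing to the participation item in Appendix F are optional clarifications. The exit-interview analysis stays as it is.

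The cost is wording only, since the plan already collects these scores. The intervals will be wide (for 21/25, about 20 points below the estimate and 11 above). A cut-off discards some information, which keeping the median and IQR offsets.

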## **10. Study Objectives/Aims:**

*Aim 1:* To pilot the ***Shauriana*** intervention among 10 participants for 3 months, in order to ensure that intervention and study procedures are optimized.

*Aim 2:* To determine the acceptability, feasibility, and safety of the ***Shauriana*** intervention and estimate initial effect size compared to standard care on PrEP uptake and adherence assessed by drug levels over 6 months in a pilot randomized controlled trial (RCT).

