Sexual identification	27-item lesbian, gay, and bisexual identity scale (LGBIS),  previously used in Kenya 	ACASI	Quarterly

Laboratory testing. HIV testing at screening and follow-up visits will be performed with two rapid tests (Determine®, Abbott Laboratories, Abbott Park, IL, USA; and First Response®, Premier Medical Corporation, Kachigam, Nani Daman, India), in accordance with the latest Kenyan HIV testing guidelines. Dried blood spots will be collected per an existing SOP at the

Anza Mapema Clinic, and stored for analysis of PrEP drug levels (i.e., detection of TFV-DP and FTC-TP), should funding permit. Safety monitoring in the RCT will be done at a higher standard than is currently available in Kenya, where costs of lab testing have prohibited routine baseline testing and instead use an approach targeted based on signs or symptoms of kidney or liver disease. Serum will be tested at baseline for creatinine level using the Cobas Integra 400 Plus biochemistry analyzer (Roche, Germany), to document normal renal function prior to PrEP start. Baseline serum will also be tested for hepatitis B surface antigen (HBsAg) using SD Bioline HBsAg WB at the CDC-KEMRI laboratory in Kisumu; men who do not have chronic hepatitis B (i.e., those who are HBsAg negative) will be offered hepatitis B vaccination.

Blood and urine aliquots from baseline, month 3, and month 6 will be stored at -80°C in the NRHS laboratory in Kisumu. Urine samples will be shipped on dry ice for testing utilizing the liquid chromatography tandem mass spectrometry (LC-MS/MS) urine tenofovir (TFV) assay developed at Philadelphia FIGHT/Children's Hospital of Philadelphia by [name] and colleagues, currently performed by Molecular Testing Labs in Vancouver, Washington, USA. This assay detects TFV with greater sensitivity than plasma-based measures, with a detection window within 7 days of the last TDF/FTC dose. In addition, dried blood spots will be shipped to Molecular Testing labs for TFV-DP and FTC-TP quantitation using LC-MS/MS to estimate the number of doses taken in the past 7 days. If any participant acquires HIV during the study, HIV-1 genotypic resistance testing will be conducted on stored samples at the CDC-KEMRI laboratory in Kisumu, to determine whether acquired virus is resistant to TDF or FTC.

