approaches will help assess the utility of the instruments used for future analyses and research in HIV-negative Kenyan GBMSM.

Given the preliminary nature of this work and the small sample size dictated by time and budget limitations, secondary analyses will focus on obtaining estimates of Table 2 secondary outcomes (PrEP uptake, adherence, refills, and drug levels) in each group and characteristics associated with these outcomes, for use in design of a larger study. Retention will be compared across study arms using uncorrected Chi square tests in an intent-to-treat analysis. Rates and patterns of self-reported PrEP adherence (defined as taking 4 or more doses per week) will be examined, and assessment methods will be compared using bivariate analyses (e.g., Spearman correlation coefficients for continuous variables). Sociodemographic and other potential cofactors will be evaluated for associations with adherence measures and other outcomes (e.g., urine TFV levels, dried blood spot TFV-DP) using Wilcoxon rank sum or independent-sample t tests, Spearman or Pearson correlations, and chi-square tests as appropriate. Multivariable analyses will adjust for sociodemographic and other potential cofactors. Parsimonious model testing will explore potential intervention efficacy.

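### Does urine tenofovir, which reflects recent dosing, undermine an adherence outcome defined as four or more doses a week?

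*Combined protocol and SAP*

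**What the plan says.** Section 10 states Aim 2 as estimating an initial effect size "on PrEP uptake and adherence assessed by drug levels over 6 months".

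Table 2 in Section 11 lists four separate secondary outcomes: PrEP uptake (ACASI), PrEP adherence (self-report by ACASI), PrEP refills (clinic records) and PrEP drug levels (laboratory). Section 13 keeps the same list: "secondary analyses will focus on obtaining estimates of Table 2 secondary outcomes (PrEP uptake, adherence, refills, and drug levels) in each group". Its only adherence definition is in the statement that "self-reported PrEP adherence (defined as taking 4 or more doses per week) will be examined". It adds that "assessment methods will be compared using bivariate analyses", giving Spearman correlation as an example.

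Two assays are named. In Section 11, under Aim 2 Procedures, "At the end of the trial, urine samples will be tested for tenofovir (TFV) drug levels", with no condition. For DBS the same paragraph says: "Dried blood spots will also be collected and stored for future testing of TFV-DP and FTC-TP levels, should funding permit". Under Laboratory testing, the urine assay is described "with a detection window within 7 days of the last TDF/FTC dose", and the spots are to be shipped "for TFV-DP and FTC-TP quantitation using LC-MS/MS to estimate the number of doses taken in the past 7 days". That shipping sentence and the one in Section 14 omit the funding condition, which appears in Aim 2 Procedures, in Table 2 and earlier under Laboratory testing.

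The only biological threshold tied to four or more weekly doses is in Section 8: 700 fmol/punch of TFV-DP in dried blood spots, used in the earlier Kisumu PrEP cohort.

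**The concern.** Aim 2 speaks of adherence measured by drug levels, yet the assay sure to be paid for shows how recently a man took a dose, not how many he took in a week. Someone taking one tablet a week can test positive. The assay that matches the four-dose definition is the DBS one, and it depends on funding. Section 13 gives no urine level that corresponds to four doses and no statement of how urine relates to the definition.

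Section 13 intends these estimates for the design of a larger study. If urine detection were carried forward as the adherence rate, the assumed control rate would be too high and an improvement from partial to adequate dosing would be understated. In the comparison of methods, a man who truthfully reports two doses a week and tests urine-positive might be taken for a misreporter.

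**Working it through.** **1. The earlier cohort's figures (Section 8).** Of 275 visits with DBS, 178 had no detectable drug and 28 were at the protective level.
- 178/275 = 64.7% and 28/275 = 10.2%, as stated.
- Detected: 275 − 178 = 97, or 35.3%.
- Detected but below the protective level: 97 − 28 = 69, or 69/97 = 71.1%.
- Detection against protective level: 97/28 = 3.5-fold.

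This shows that detection and four-dose adherence can differ greatly in this population. It does not size the gap for urine: these are pooled DBS visits, and the documents give no urine rates.

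**2. What detection alone would show.** Assume that each day's dose is taken independently with probability k/7, where k is the average number of doses a week, and that urine is positive if any dose fell in the last w days. The documents support w = 7 as the outer limit; w = 3 is an assumed lower value.

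P(detected) = 1 − (1 − k/7)^w

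P(four or more doses in a given week) = P(X ≥ 4), X ~ Binomial(7, k/7)

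| k | detected, w = 7 | detected, w = 3 | four or more doses that week |
|---|---|---|---|
| 0 | 0% | 0% | 0% |
| 1 | 66.0% | 37.0% | 1.0% |
| 2 | 90.5% | 63.6% | 10.8% |
| 3 | 98.0% | 81.3% | 34.7% |
| 4 | 99.7% | 92.1% | 65.3% |

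Gain in percentage points on moving to an average of four doses a week:

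| from | urine, w = 7 | urine, w = 3 | four-dose definition |
|---|---|---|---|
| 0 | 99.7 | 92.1 | 65.3 |
| 1 | 33.7 | 55.1 | 64.3 |
| 2 | 9.2 | 28.6 | 54.5 |
| 3 | 1.7 | 10.8 | 30.6 |

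Detection is weak for men already taking two or three doses. The fair benchmark for it is the last column, not 100 points, because the weekly definition does not register every such move either. For men starting from nothing, detection responds strongly. That contrast is important here: Section 11 admits only men who have not taken PrEP in the past 3 months, and 64.7% of the earlier cohort's visits showed no drug.

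**3. Does the plan make the substitution?** Table 2 has one row for self-reported adherence and another for drug levels, and the Section 13 list keeps them apart. The four-dose definition qualifies self-report only. Nowhere is a urine result converted to adherent or non-adherent. The plan also speaks of urine levels, measured by LC-MS/MS and analysed with rank and correlation methods, so the percentages in step 2 apply only if an analyst reduces the level to detected or not.

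**4. The comparison of methods.** Section 13 proposes to compare measures, not to label men as misreporters. The disagreement that mattered in the earlier cohort was high self-report (median 98% on the visual analogue scale) with no drug found. Urine can still show that pattern: if the 7-day window holds, a man with no detectable urine drug has not taken four doses in the past week.

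**The case for a change.** The strongest case for a change is that Aim 2 does say adherence is measured by drug levels, so without a stated link the aim has no defined drug-level adherence outcome. A correlation between methods supplies no classification rule. Self-report cannot fill the place either, since it was badly inflated in the earlier cohort. One paragraph would settle the matter before results are seen: name urine as the lead measure of recent dosing, reserve the four-dose definition for DBS, and state the visit contrast, effect measure and handling of replaced men and missing samples.

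Part of this stands. The wording of Aim 2 is looser than Table 2, and if the spots are never assayed the trial will have no drug-level estimate on the four-dose scale. But that follows from funding, and no sentence in Section 13 would supply the missing estimate. The remaining requests are reporting details for secondary outcomes that Section 13 treats as estimation and that Section 11, under Power considerations, says the trial is not powered to test.

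One possible change of method is to assay stored spots only where urine is positive. At month 3 and month 6 that would be about 60 × 2 × 97/275 = 42 of 120 assays, if the DBS detection rate carried over to urine. It still needs money that is not secured. With a 3-day window it would also miss 100 − 92.1 = 7.9% of men averaging four doses a week.

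**Conclusion.** The concern does not call for a change. Urine tenofovir and the four-dose definition do measure different things, but the plan reports them as different outcomes, and the harm arises only if a later reader merges them. Followed as written, the plan gives valid urine results by arm that describe recent dosing. An analyst who reads the assay description in Section 11 would label them so and apply the 700 fmol/punch threshold to DBS if those are run. The mixed funding wording on DBS is a clerical inconsistency: the condition appears in three places, including earlier under Laboratory testing, and the shipping sentences are naturally read as subject to it.

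If urine were reduced to detected or not, its gain on moving to four doses a week would be 1.7 to 55.1 points for men already taking one to three doses, against 30.6 to 64.3 for the definition, and 92.1 to 99.7 points for men taking none. These figures rest on independent daily dosing and a window of 3 to 7 days; the documents supply only the 7.
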